7.9 Table of trial procedures

	Screening phase	Treatment phase				Follow up phase		
		Study Day 1	Morning of Study Day 2	Morning of Study Day 3	Morning of Study Day 4 ¹⁵	Discharge	Re-admission	3 Months after study start dose
Informed consent	X							
In- and exclusion criteria	X							
Randomization	X							
Demographics ¹	X							
Medical history	X							
Vitals ²	X		X	X	X			X
Weight ¹²	X		X	X	X	X		X
EQ5D	X				X		X ¹¹	X
Volume assessment	X		X ¹⁶	X ¹⁶	X ¹⁶	X		X
Study treatment		X ³	X ⁴	X ⁴				
Urinary collection ⁵		X	X	X				
Local lab	X ⁶		X ⁷	X ⁷	X ⁷			X ⁷
Laboratory sub-study ¹³ blood	X				X ¹⁴			X
Laboratory sub-study ¹³ Urine			X	X				
Plasma BNP or NT-proBNP ⁸	X				X			X
Urine pregnancy testing ⁹	X							
Concomitant medication ¹⁷	X	X	X	X	X	X		X
Adverse Events ¹⁰	X	X	X	X	X	X	X	X

- 1) Age, race and ethnicity
- 2) Arterial blood pressure and heart rate
- 3) Start dose (IV) = 2 x orally daily maintenance dose of loop diuretics and 500 mg acetazolamide or placebo (see section 8)
- 4) As long as patient is volume overloaded, Treatment dose (IV) = 1x orally daily maintenance dose of loop diuretics and 500 mg acetazolamide or placebo between 8:00 and 12:00 and a second dose minimum 6 hours later with again 1x orally daily maintenance dose (see section 8)
- 5) See [appendix 4](#)
- 6) Serum hemoglobin, hematocrit, electrolytes (Na, K, Cl, HCO₃), serum osmolality, serum urea, serum Cr, total protein, serum albumin, Fe, ferritin, TSAT, LDH, troponin and eGFR
- 7) Serum hemoglobin, hematocrit, electrolytes (Na, K, Cl, HCO₃), serum urea, serum Cr and serum albumin

- 8) Protocol requires that plasma levels of BNP or NT-proBNP are collected. In case the patient is on succubutril/valsartan, it is mandatory that NT-proBNP plasma levels are determined on the blood sample.
- 9) Only pre- menopausal women who are not surgically sterile, as well as women of childbearing potential.
- 10) Safety reporting flow is documented in section 9
- 11) EQ5-D needs to be collected once during any readmission (as soon as possible during readmission))
- 12) Measurement of body weight should be performed as consistently as possible using a standardized scale, preferably with a precision of 50 g, in the morning, post-void, prior to eating, prior to the medication dose, and with patients wearing the same clothing. The scales should stand on a flat, solid surface rather than carpets unless specifically designed for use in that setting
- 13) Blood and urine will be collected in a subset of randomized patients participating in the laboratory sub-study. Blood will be collected on screening, day 4 or at discharge (whatever comes first) and 3 month FU visit. Urine sample will be collected from Urinary Collection period 1 and Urinary collection period 2 (see also appendix 4).
- 14) In case day 4 falls into a weekend or public holiday, blood collection for sub-study can also be done on day 5 or day 6. If a patient is being discharged before the morning of day 4, blood collection for the sub-study should occur at discharge.
- 15) In case discharge is earlier than the morning of day 4, all assessments of day 4 should be performed at discharge.
- 16) As long as patient was assessed volume overloaded during the previous volume assessment a volume assessment needs to be performed
- 17) See [appendix 5](#)

7.10 Laboratory sub-study

Blood samples and urine samples from centers who agreed to participate in the Laboratory sub-study will be collected during the Advor trial. All potential patients at these centers will be asked to participate in the laboratory sub-study. An additional signed and dated informed consent must be obtained before the additional blood and urine samples will be collected.

The right of a participant to refuse participation without giving reasons must be respected. The participant must remain free to withdraw at any time from this sub-study without giving reason and without prejudicing his/her further treatment and will be provided with a contact point where he/she may obtain further information about the sub-study. Where a participant is required to re-consent or new information is required to be provided to a participant it is the responsibility of the PI to ensure this is done in a timely manner.

All patients enrolled in the laboratory sub-study will have blood collected on screening, day 4 and during the 3 month follow up visit. In case the patient is being discharged before the morning of day 4, blood samples should be collected at discharge. The collected blood samples will be shipped to the University Biobank Limburg for storage and additional research. Urine samples collected from the Urinary Collection period 1 and from the Urinary Collection period 2 ([see appendix 4](#)) will be shipped to the University Biobank Limburg for storage and additional research.

Biomarkers related to cardiac and renal function/injury will be obtained from blood and urine in the subset of patients participating in the laboratory sub-study. Biomarkers will be used to elucidate the effect of acetazolamide and to explore drug effect versus baseline biomarkers of risk. Biomarkers of potential interest are NT-proBNP, Galectin 3, ST2, Cystatin C and NGAL. The list of potential biomarkers may be changed or expand further as it is recognized that more relevant or novel biomarkers may be discovered. Biomarkers may be measured during the process of this study or after its completion. No genetic analysis will be performed with the collected sub-study samples. Detailed sample handling instructions will be provided in a separate laboratory manual.

7.11 Withdrawal criteria

All subjects will be encouraged to remain on treatment and under observation for the full duration of the study. However, at any time during the study and without giving reasons, subjects may withdraw from the study at their own request or at the request of their legally acceptable representative. The subject will not suffer any disadvantage as a result.

It is important to note that discontinuation of study treatment (see section 8) is not the equivalent to withdrawal of informed consent. In cases where subjects indicate they do not want to "continue", investigators must determine whether this refers to discontinuation of study treatment (the most common expected scenario), unwillingness to attend the follow-up visit, unwillingness to have telephone contact, unwillingness to have any contact with study personnel, or unwillingness to allow contact with a third party (e.g., family member, doctor). Every effort must be made to continue to follow the subject until the end of the study.

In all cases, the reason for discontinuation (including "at the subject's request") must be recorded in the case report form (CRF) and in the subject's medical records.

No subject replacements are permitted in the study.

7.12 End of trial

The Sponsor's CTU ZOL will notify the FAMHP and main EC of the end of a clinical trial within 90 days of its completion date (last patient last visit).

8 TRIAL INTERVENTION / MEDICATION

The ADVOR study is a phase IV randomized, multi-center, double-blind study, comparing monotherapy with high-dose loop diuretics and placebo (standard of care - SOC) versus combination therapy with acetazolamide and high-dose loop diuretics in patients with decompensated heart failure and clinical signs of volume overload.

8.1 Name and description of intervention(s)

At randomization

At the moment of randomization, oral loop diuretics are stopped and the patient receives an IV bolus of loop diuretics at a dose equal to the double of his oral daily maintenance dose* with a maximal dose of 5 mg bumetanide (=200 mg furosemide). Bumetanide is the preferred loop diuretic agent to be used in this trial.

Conversion factor:

1 mg bumetanide po = 1 mg bumetanide IV

40 mg furosemide po = 40 mg furosemide IV

20 mg torsemide po = 40 mg furosemide IV = 1 mg bumetanide IV

Some examples are listed below:

- *if a patient takes 1x1 mg bumetanide po, the patient will receive 2x1x1 mg = 2 mg bumetanide IV*
- *if a patient takes 2x2,5 mg bumetanide po, the patient will receive 2x2x2,5 mg = 5 mg bumetanide IV*
- *if a patient takes 1x40 mg furosemide po, the patient will receive 2x1x40 mg = 80 mg furosemide IV*
- *if a patient takes 1x80 mg furosemide po, the patient will receive 2x1x80 mg = 160 mg furosemide IV*
- *if a patient takes 1x20 mg torsemide po, the patient will receive 2x1x1 mg bumetanide IV = 2 mg bumetanide IV or 2x1x40 furosemide IV = 80 mg furosemide IV*

Together with this initial dose of loop diuretics patients will receive an intravenous bolus of 500 mg of acetazolamide or placebo.

START DOSE (IV) = 2 x orally daily maintenance dose* of loop diuretics (max. 5 mg of bumetanide)

+

500 mg acetazolamide or placebo

**If the oral daily maintenance dose has changed over the week prior to randomization, it will be defined as the highest orally administered daily dose that the patient has received in an outpatient context 3 days prior to randomization.*

During the treatment phase

[figure not shown]
Between administering the start dose and next treatment dose a minimum of 6 hours is required. During the remaining part of the treatment phase, the patient will continue to receive 2 treatment doses every day provided that the treating physician has concluded during the morning rounds that the patient is still volume overloaded (see Figures 2+3). The dose will be the orally daily maintenance dose, administered between 8:00 and 12:00 am, together with an intravenous bolus of 500 mg of acetazolamide or placebo. The second dose of loop diuretics, again the orally daily maintenance dose, will be given 6 hours after the morning dose.

Any patient with more than trace oedema, residual pleural effusion or residual ascites would be considered to be still volume overloaded (see Figures 2 + 3). Residual pleural effusion and/or ascites should always be confirmed by chest X-ray or echography. If pleural effusion/ascites is used as an inclusion criteria, chest X-ray and/or echography should be repeated until decongestion has been achieved (volume assessment score ≤ 1). If not present at inclusion, new evidence of pleural effusion and/or ascites may arise during the treatment phase, but if scored, it should be confirmed by a chest X-ray or echography. If the patient is not volume overloaded anymore, the intravenous administration of study medication should be stopped. Once decongestion is achieved (volume assessment score ≤ 1) during the treatment phase, no volume assessment should be performed the following morning.

Between 8:00 and 12:00 am TREATMENT DOSE (IV) = 1x orally daily maintenance dose (max. 5 mg of bumetanide)
+
500 mg acetazolamide or placebo

6 hours later TREATMENT DOSE (IV) = 1x orally daily maintenance dose

Figure 2. Flow chart to guide study.

After treatment phase

After the treatment phase, treating physicians are recommended not to prescribe oral acetazolamide as a maintenance diuretic therapy after decongestion; instead, they are encouraged to restart the original oral maintenance dose of loop diuretics when the patient was still stable. Patients can be discharged as early as 24 hours after the physician concluded that the volume overload is no longer present. An outpatient follow-up appointment is scheduled at least 3 months (90 days) (with a window of + 14 days) after the start of study medication. It is mandatory to perform a volume assessment at discharge and at follow-up. It is recommended to perform a chest X-ray or echography in case of clinical signs of pleural effusion or ascites, yet, it will be left to the discretion of the treating physician.

STOP TREATMENT

The treating physician is allowed (but not obliged) to stop the study treatment, which counts as treatment failure **in case of persistent volume-overload** in following cases:

- symptomatic hypotension with a systolic blood pressure <100 mmHg
- asymptomatic hypotension with a systolic blood pressure <90 mmHg
- an increase of serum Cr levels x 1.5 of the serum Cr level compared to admission value.
- Occurrence of metabolic acidosis (ph < 7.2)

If any of these events occur when the patient is judged to be euvolemic, the study treatment is stopped and stopping is not considered a treatment failure.

[figure not shown]
Freedom from volume-overload (i.e. congestion) on the morning of day 4 will be defined as not more than trace oedema, no residual pleural effusion, and no residual ascites (Figure 3)

Figure 3: Volume assessment

OEDEMA	No oedema (score 0)	Trace oedema (pitting disappear immediately) (score 1)	Clear pitting oedema (score 2)	Visual deformation above ankle (score 3)	Visual deformation above knee (score 4)
PLEURAL EFFUSION (to be confirmed by chest X-ray or ultrasound on admission if suspected)	No pleural effusion (score 0)	Minor (non-amendable for puncture) pleural effusion (score 2)		Major (amendable for puncture) pleural effusion (score 3)	
ASCITES (to be confirmed by ultrasound on admission if suspected)	NO ascites (score 0)	Minor ascites, only detected by echography (score 2)		Significant ascites (score 3)	

Succesfull decongestion

Continue IV diurectic therapy

Treatment DOSE ADJUSTMENTS in case of an inappropriate diuretic response

If the total urinary output (see Figure 1 and [Appendix 4](#)) on the morning of day 3 is < 3500 mL and the patient is still volume overloaded, an escalation of decongestive treatment is mandatory. One of the outlined three options can be chosen at the discretion of the treating physician.

Escalation therapy options:

- doubling of the IV dose of the loop diuretics
- add oral chlorthalidone 50 mg once daily
- ultrafiltration or renal replacement therapy might be considered

The decision to proceed with escalation therapy needs to be collected in the case report form as the patient needing escalation cannot reach the primary endpoint.

Background therapy

24h oral intake of fluid and sodium will be restricted to 1500 mL and 1.5 g, respectively. It is recommended that all patients receive the same maintenance infusion with 500 mL glucose 5% and 3g MgSO₄ administered over 24h time interval, until complete decongestion or end of the study treatment phase. All non-protocol fluids administered (including those for administration of intravenous medication) should be limited.

In case of **serum potassium levels <4 mmol/L**, 40 mmol of KCl is added to the maintenance infusion. Oral potassium supplements may be used at the discretion of the treating physician, but their use will be prospectively registered.

In case of **metabolic acidosis** with serum bicarbonate levels <20 mmol/L, it is recommended to administer intravenously 100 ml of NaHCO_3 8.4%.

Treatment with **neurohumoral blockers** (e.g. renin-angiotensin system blockers, sacubitril/valsartan, beta-blockers, and mineralocorticoid receptor antagonists) may be continued at the same or lower dosage at the discretion of the treating physician, until the end of the treatment phase (max 4 days) or until complete decongestion is achieved, whatever comes first. Dose increases for any of these medications are not allowed during the screening and treatment phase with the exception of mineralocorticoid receptor antagonists in case of hypokalaemia despite intravenous potassium supplement. In addition, starting an SGLT2 inhibitor and a switch from renin-angiotensin system blockers to sacubitril/valsartan is not allowed during the screening and treatment phase, but might be pursued after decongestion is achieved. After decongestion, it is strongly recommended to up-titrate doses of neurohumoral blockers according to the guidelines in the HFrEF patients. Dosages of neurohumoral blockers are collected at screening, at discharge and at three months follow-up.

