RCT	Randomised Clinical Trial
RRT	Renal replacement therapy
SD	Source document
SI	Sub-investigator
SOC	Standard of care
TMG	Trial Management Group
TSC	Trial Steering Committee

VAS	Visual analogue scale
WRF	Worsening renal function
ZOL AV	Ziekenhuis Oost Limburg Autonome Verzorgingsinstelling

TRIAL FLOW CHART

Figure 1. Trial flow Chart.

*bumetanide is preferred loop diuretic agent
 Conversion factor is 1 mg bumetanide = 20mg torsemide = 40 mg furosemide (IV and oral)
 Bolus of bumetanide is limited to 5 mg bumetanide

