4.3 Intervention

At the moment of randomization, oral loop diuretics are stopped and the patient receives an IV bolus of loop diuretics at a dose equal to the double of his oral daily maintenance dose with a maximal dose of 5 mg bumetanide (=200 mg furosemide). Bumetanide is the preferred loop diuretic agent to be used in this trial. Between administering the start dose and next treatment dose a minimum of 6 hours is required. During the remaining part of the treatment phase, the patient will continue to receive 2 IV treatment doses every day provided that the treating physician has concluded during the morning rounds that the patient is still volume overloaded (see Figures 2, volume assessment score > 1). The IV loop diuretic dose will be the orally daily maintenance dose, administered between 8:00 and 12:00 am, together with an intravenous bolus of 500 mg of acetazolamide or placebo. The second dose of IV loop diuretics, again dosing equal to the orally daily maintenance dose, will be given 6 hours after the morning dose. Any patient with more than trace oedema, residual pleural effusion or residual ascites would be considered to be still volume overloaded (see Figures 2). Residual pleural effusion and/or ascites should always be confirmed by chest X-ray or echography. If pleural effusion/ascites is used as an inclusion criteria, chest X-ray and/or echography should be repeated until decongestion has been achieved (volume assessment score ≤ 1). If not present at inclusion, new evidence of pleural effusion and/or ascites may arise during the treatment phase, but if scored it should be confirmed by a chest X-ray or echography. If the patient is not volume overloaded anymore, the intravenous administration of study medication should be stopped. Once decongestion is achieved (volume assessment score ≤ 1) during the treatment phase, no volume assessment should be performed anymore the following morning.

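### Protocol v2.0 limits a bumetanide bolus to 5 mg but prints no cap on the second daily dose or the day-3 doubling, so for home doses above 2.5 mg/day the stated dosing rules cannot all be followed as written

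*Combined protocol and SAP*

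**What the plan says.** The following texts of protocol v2.0 and SAP v2.0 bear on the size of a loop diuretic bolus.

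- **Protocol, note under Figure 1 (Trial Flow Chart):** "Bolus of bumetanide is limited to 5 mg bumetanide". The sentence is not tied to any particular dose.
- **Protocol 8.1, start dose:** twice the oral daily maintenance dose, "with a maximal dose of 5 mg bumetanide (=200 mg furosemide").
- **Protocol 8.1, morning treatment dose:** "TREATMENT DOSE (IV) = 1x orally daily maintenance dose (max. 5 mg of bumetanide").
- **Protocol 8.1, second treatment dose, printed directly below:** "6 hours later TREATMENT DOSE (IV) = 1x orally daily maintenance dose". No cap is printed.
- **Protocol 8.1, first escalation option on day 3:** "doubling of the IV dose of the loop diuretics". No cap is printed. SAP 4.3.2 repeats this option, also without a cap.
- **Protocol 7.9, footnotes 3 and 4:** the start dose and both daily doses are given without a cap, with a reference to section 8.
- **SAP 4.3:** the cap is printed for the start dose only. For the afternoon dose it says "The second dose of IV loop diuretics, again dosing equal to the orally daily maintenance dose, will be given 6 hours after the morning dose".

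Eligibility (protocol 6.1) sets a minimum home dose of 1 mg bumetanide or equivalent and no maximum. One of the protocol's own worked examples is a patient at 5 mg/day.

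**The concern.** When two adjacent dose lines are printed and only one carries the cap, a site can reasonably conclude that the other is uncapped. The note under Figure 1 points the other way. Both readings are defensible, and for patients on high home doses they give different boluses.

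The same holds for the doubling option. Escalation is mandatory when the day-3 criterion is met, so a physician who chooses doubling for such a patient must either go above a limit that the protocol states or stop short of the doubling that the protocol describes.

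Three things are at stake: the dose that a patient receives, what counts as a protocol deviation, and the consistency of recorded loop diuretic exposure across sites. The last matters because total IV loop dose over the first four days is an exploratory endpoint (SAP 4.1.5) and a lower total loop dose is part of the primary objective as worded in SAP 4.1.2.

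**Working it through.** **Inputs.** D is the oral daily maintenance dose in mg bumetanide. The limit is 5 mg per bolus (Figure 1 note; 8.1 for the start and morning doses). The conversion is 1 mg bumetanide = 40 mg furosemide (8.1).

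**Reproducing the plan's figures.** 5 × 40 = 200 mg furosemide, as printed. For the worked example at D = 5 ("if a patient takes 2x2,5 mg bumetanide po, the patient will receive 2x2x2,5 mg = 5 mg bumetanide IV"), the product is 2 × 2 × 2.5 = 10 mg. The printed 5 mg is the capped result, min(10, 5). The equation is wrong as printed, but the cap stands in the paragraph above it and in the start-dose box below it, so the dose meant is clear. This is clerical.

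**Rules as printed in v2.0.**

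- Start dose = min(2D, 5).
- Morning dose = min(D, 5).
- Second dose = D as written, or min(D, 5) if the Figure 1 limit governs it.
- Doubled dose = 2 × the current dose as written, or the smaller of that and 5 if the limit governs it.

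| D (mg/day) | Start | Morning | Second, as written | Doubled, as written (morning / second) | Doubled, limit applied | Ratio of limited doubled dose to morning dose |
|---|---|---|---|---|---|---|
| 2 | 4 | 2 | 2 | 4 / 4 | 4 | 2.00 |
| 2.5 | 5 | 2.5 | 2.5 | 5 / 5 | 5 | 2.00 |
| 3 | 5 | 3 | 3 | 6 / 6 | 5 | 1.67 |
| 4 | 5 | 4 | 4 | 8 / 8 | 5 | 1.25 |
| 5 | 5 | 5 | 5 | 10 / 10 | 5 | 1.00 |
| 6 | 5 | 5 | 6 | 10 / 12 | 5 | 1.00 |
| 8 | 5 | 5 | 8 | 10 / 16 | 5 | 1.00 |
| 10 | 5 | 5 | 10 | 10 / 20 | 5 | 1.00 |

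**Reading the table.**

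- D up to 2.5: no conflict. A full doubling stays within 5 mg.
- D between 2.5 and 5: doubling as written goes above the limit. Held to the limit, it is a real but smaller increase.
- D of 5 or more (200 mg furosemide or more): doubling as written gives at least 10 mg per bolus. Held to the limit, the dose does not change. At D = 5 the two readings differ twofold, 10 mg against 5 mg per bolus, or 20 mg against 10 mg per day.
- D above 5: the second daily dose as written exceeds both the limit and the morning dose, for example 6 mg against 5 mg at D = 6.

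**Daily total on days 2 and 3, before any escalation.** At D = 4 it is 4 + 4 = 8 mg, and at D = 5 it is 5 + 5 = 10 mg. Both equal 2D. Only above 5 mg/day does it fall below 2D: at D = 6, as written, 5 + 6 = 11 mg against 12 mg.

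**The case against.** The strongest reply is that the Figure 1 note is general. It can be read as already covering every bolus, and silence elsewhere does not cancel it. The footnotes in 7.9 defer to section 8, and SAP 4.3 only summarises the regimen. For the second daily dose this has force: the gap is an omission that becomes a conflict only above 5 mg/day, and only if the line is read as uncapped. The bodies of Figures 1 and 2 were not available in the text reviewed and may carry further wording on the cap. The reply does not settle the doubling option. If the limit applies there, the option as described cannot be carried out above 2.5 mg/day, and nothing in the documents says what replaces it.

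Some stronger readings are tempting, but the documents do not support them.

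- *That every patient on a high home dose either breaches the limit or gets an escalation that does nothing.* No change is exact only at 5 mg/day or more; between 2.5 and 5 mg/day the limited dose still rises. Doubling is also one of three options at the physician's discretion, and the other two do not depend on the bumetanide limit.
- *That comparability with the high-dose arm of the DOSE trial is lost.* Up to 5 mg/day the day 2 and day 3 totals remain twice the home dose. The lower start dose comes from a cap that 8.1 and SAP 4.3 state consistently, not from this ambiguity.
- *That the primary analysis is biased.* A patient needing escalation is a failure whatever dose follows. Differences between sites in reading the rule arise under blinding, with randomisation blocked by centre and a random centre effect in the model. One narrow route remains: above 5 mg/day, the uncertain second bolus on day 2 falls inside the urine collection that feeds the 3500 mL criterion. Nothing suggests that this would differ by arm.

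**Conclusion.** The inconsistency is real and confined to high home doses. For home doses above 2.5 mg/day, the doubling option as written and the 5 mg bolus limit cannot both be followed. At 5 mg/day or more, including the protocol's own example patient, doubling either gives boluses of 10 mg or more or leaves the dose where it was. Above 5 mg/day the second daily dose has the same problem if read as uncapped.

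The number of patients concerned cannot be computed, because the documents do not give the distribution of home doses. The sample size, and the classification of escalated patients as failures, are unaffected. The consequences are for dosing clarity and patient safety at site level, for what is recorded as a deviation, and for the total IV loop dose endpoint. The conclusion rests on the text of v2.0 as available and assumes that the figures carry no further cap wording.

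**What to change.** The sponsor should reconcile the Figure 1 note, protocol 7.9 (footnotes 3 and 4), protocol 8.1 (start dose, both daily doses and the escalation options) and SAP 4.3 and 4.3.2. One statement, used in all of these places, should say:

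1. which boluses the 5 mg limit covers, naming the second daily dose and the doubled dose explicitly; and
2. what the doubling option means for a patient whose doubled dose would exceed the limit, including one already at it.

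The sponsor decides the rule; this review takes no position on it. The 2 × 2.5 mg example can be corrected at the same time, so that the line shows 10 mg reduced by the cap.

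The cost is a protocol clarification and a matching SAP edit. A descriptive table of delivered loop dose relative to home dose, by arm and with capped patients flagged, would be a useful option. It needs no new data, since diuretics are already recorded under protocol Appendix 5.
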